### Cohort 1: *Boostrix*-Exposed group

#### Inclusion Criteria

- Currently pregnant women at the time of enrollment who contacted the OTIS/MotherToBaby Research Center and who have documented exposure to *Boostrix* brand Tdap vaccination on or after the 1st day of the 27th week of pregnancy.

- Currently pregnant women at the time of enrollment who agreed to the conditions and requirements of the study including informed consent, the interview schedule and release of medical records.
- Availability of obstetric, delivery and pediatric medical records for the enrolled pregnancy

#### Exclusion Criteria

- Women who have previously been included in this study with a prior pregnancy.

### **Cohort 2: Tdap Vaccine-Unexposed Comparator Group**

#### Inclusion Criteria

- Currently pregnant women at the time of enrollment who were not exposed to any Tdap vaccine from the first day of LMP to the end of pregnancy.
- Currently pregnant women at the time of enrollment who agree to the conditions and requirements of the study including informed consent, the interview schedule and release of medical records.
- Availability of obstetric, delivery and pediatric medical records for the enrollment pregnancy.

#### Exclusion Criteria

- Women who have received a Tdap vaccine anytime during pregnancy.
- Women who have previously been included in this study with a prior pregnancy.

### **7.2.2. Study conduct**

The study will be conducted by investigators at the University of California OTIS/MotherToBaby Research Center. The OTIS/MotherToBaby organization is a network of university and health department based telephone information centers serving pregnant women and health care providers throughout the US (Leen-Mitchell, 2000). These services receive spontaneous telephone inquiries from women who are pregnant or considering pregnancy as well as from health care providers about the safety or risk associated with environmental exposures in pregnancy, including medications and vaccines. Trained Teratogen Information Specialists at each site provide appropriate risk assessment and referral for all patient and health care provider callers free of charge. These services also provide a basis for collaborative research such as this study. Thus, individual Teratogen Information Services located throughout the US serve as a primary source of referrals not only for *Boostrix*-exposed pregnancies but also for similarly ascertained pregnant women with no exposure to Tdap vaccination during pregnancy.

Other methods of raising awareness about the study are meeting exhibits at professional practice meetings nationally, regionally, and locally, direct mail to health care providers, media, social media, and website. Awareness activities will also be directed to maternal-fetal medicine specialists, obstetricians, primary care physicians (PCP), and other specialists caring for pregnant patients.

The GSK package labeling for *Boostrix* in the US contains information about the pregnancy exposure registry and encourages healthcare providers to register patients by calling the toll-free study number.

In addition, the American Academy of Allergy, Asthma, and Immunology as the study collaborator through the Vaccines and Medications in Pregnancy Surveillance System (VAMPSS) will be asked to promote recruitment among colleagues. The existing toll-free number for North American callers currently being utilized by all OTIS/MotherToBaby Pregnancy Studies [contact]) will be promoted.

The existing OTIS/MotherToBaby Pregnancy Registry contact and referral information is available on the study website and multiple methods are used to increase awareness through the website (<https://mothertobaby.org/pregnancy-studies/>), social media and print advertising. The US Food and Drug Administration (FDA) website (<http://www.fda.gov/womens/registries/default.htm>) lists the OTIS/MotherToBaby Pregnancy Studies and will have this Registry added to their listing. The study will also be listed on [ClinicalTrials.gov](http://ClinicalTrials.gov).

Information on the Registry will also be made available 1) in GSK product literature and promotional materials, and 2) via a link from the GSK website. Additional venues for publicizing the Registry include: 1) linking the Registry website to other specialty provider and maternal health interest websites, 2) posting notices in appropriate journals, and 3) later, presenting Registry data at obstetrics-related scientific and clinical meetings. The Sponsor will also provide information about the Registry at appropriate professional meetings. The Sponsor may facilitate awareness among prescribers through Medical Science Liaisons. The Sponsor will encourage exposed women or their Healthcare Providers to contact the Registry directly.

Pregnant women are entered in a cohort at the time of enrollment into the OTIS/MotherToBaby Pregnancy Registry. Information is collected on their pregnancy to date, and they are then followed for the duration of their pregnancy. In addition, infants will be followed for the specified safety events up to 2 months of age.

Depending on the gestational timing of enrollment, subsequent telephone interviews will be conducted according to the Schedule shown in [Table 3](#) Section 7.4. Follow up interviews will be conducted by telephone, and medical records for both the women and infant will be obtained and abstracted for information to validate exposures and outcomes.

The participants may reside anywhere in the US, and may be of any age. Those who are under 18 years of age at the time of enrollment may enroll with parent/guardian consent.

Upon study initiation, eligible participants from existing OTIS/MotherToBaby Registry data will be identified, and recruitment of newly enrolled participants is expected to continue for 4 years, or until the target of 1,500 women exposed to *Boostrix* is reached, whichever comes first. After recruitment of the last participant, infant follow-up will continue for 2 months after the last live birth. Given the prevalence of *Boostrix* vaccination in pregnancy, and annual rates of enrollment of between 1,500 and 2,000 pregnant women overall in all MotherToBaby Pregnancy Studies, the planned four-year

recruitment period for this study is reasonable. However, should recruitment numbers fail to meet targets, specific additional awareness and marketing efforts will be initiated by the MotherToBaby research team.

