## 7. RESEARCH METHODS

### 7.1. Study Design

This study is an observational cohort study of pregnancy and neonatal/early infancy safety outcomes in pregnant women in the OTIS/MotherToBaby Pregnancy Registry who received the *Boostrix* vaccine any time on or after the 1st day of the 27th week of pregnancy. The comparator cohort includes pregnant women who received no Tdap vaccine from the first day of LMP to the end of pregnancy. The incidence rates of

maternal and infant outcomes for pregnancies exposed to the *Boostrix* vaccine on or after the 1st day of the 27th week of pregnancy until the end of pregnancy will be compared to those observed in a comparator cohort unexposed to any Tdap vaccine during pregnancy. The target sample size for the study by the end of a four-year recruitment period is 3,000 participants: 1,500 pregnant women in the *Boostrix* vaccine exposure cohort and 1,500 pregnant women in the Tdap vaccine-unexposed comparator cohort.

The study will be conducted by OTIS/MotherToBaby Research Center located at the University of California San Diego. The registry relies on voluntary reporting of pregnancy and exposures by women and health care providers who contact the North American OTIS/MotherToBaby Pregnancy Studies, or the MotherToBaby network.

The study design is appropriate for the study objectives in that mothers are enrolled in the OTIS/MotherToBaby Registry before the outcome of pregnancy is known, direct measures of relative and absolute risk can be computed, and a range of adverse pregnancy outcomes can be evaluated.

The study design includes the identification of women with *Boostrix* vaccine exposure on or after the 1st day of the 27th week of pregnancy, and a comparison group without exposure to a Tdap vaccine from the first day of LMP to the end of pregnancy.

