### 7.2.1. Inclusion/exclusion criteria

All participants must meet the following criteria to be eligible for inclusion in the study:

- Reside in the US at the time of enrollment
- Enrolled in the OTIS/MotherToBaby Pregnancy Registry and currently pregnant at the time of enrollment on or after 08 March 2004
- Pregnancy ending in either livebirth or stillbirth
- Availability of medical records for that pregnancy including from obstetric provider, hospital of delivery and pediatric provider

The study sample will consist of approximately 600 participants in each cohort that have previously been enrolled in the OTIS/MotherToBaby Pregnancy Registry before the end of pregnancy, have completed their pregnancies with either a livebirth or stillbirth outcome, and have sufficient medical record and exposure data to meet the study objectives. An additional 1,800 participants (900 in each cohort) will be enrolled over four years; these participants will enroll before the end of pregnancy, have completed their pregnancies with either a livebirth or stillbirth outcome, and have sufficient medical record and exposure data to meet the study objectives.

- Selection for consideration for inclusion of the 600 pregnancies in each cohort from those previously enrolled in the OTIS/MotherToBaby Pregnancy Registry will be made solely on the following criteria irrespective of pregnancy outcome
  - Pregnancy continuing as of the 1st day of the 27th week of gestation
  - Availability of data on Tdap vaccination status on or after the 1st day of the 27th week of gestation
  - If vaccinated, data available to document Tdap vaccination brand
  - Availability of the required medical records from obstetric, hospital and pediatric providers
  - Selection starting with most recent year of enrollment until sample size is met

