#### 7.4. Data sources

Teratogen Information Services (MotherToBaby sites) provide referrals from pregnant women who call and who are interested in participating in the OTIS/MotherToBaby Pregnancy Registry. Healthcare providers are also informed that patients with Tdap exposure can be referred to the OTIS /MotherToBaby Pregnancy Registry. Active recruitment strategies are also used, e.g., direct mailings to healthcare providers, website, and professional meetings.

Enrollment in the OTIS/MotherToBaby Pregnancy Registry is voluntary and requires informed consent by the pregnant woman. The OTIS/MotherToBaby Research Center is responsible for verifying the participant selection criteria, enrolling each participant, and securing informed consent, providing all pregnancy and post-partum follow-up interviews and medical record review, recording and storage of all data, and subsequent data analysis and interpretation.

As part of the OTIS/MotherToBaby Pregnancy Registry protocol, data are collected using maternal interview(s), medical record review (obstetric, delivery hospital, pediatric, and vaccine provider, if applicable), and the pregnancy exposure diary (Table 3). The exposure diary is used as a supplemental source of information about medications, vaccines taken or received in pregnancy.

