#### **7.5. Study size**

[figure not shown]
The target sample sizes in each of the study cohorts are as follows:

- 1,500 women exposed to *Boostrix* on or after the 1st day of the 27th week of gestation through the end of pregnancy
- 1,500 women unexposed to any Tdap vaccine throughout their pregnancy

Including an estimated 600 eligible participants per cohort already enrolled in the OTIS/MotherToBaby Pregnancy Registry, enrollment of 1,500 participants in each of the cohort groups is planned for completion within 4 years. Participants are eligible to enroll at any time in pregnancy including prior to the gestational timing of the recommended Tdap vaccine. (Examples of gestational timing of enrollment, exposure, and outcome are shown in [Figure 1](#) and [Figure 2](#)). Thus, some initially enrolled pregnancies will no longer be eligible for analysis due to pregnancy losses (spontaneous abortion, elective termination, stillbirth prior to the 27th week of gestation, or lost-to-follow-up). Additionally, some pregnancies will not be eligible for inclusion due to failure to release medical records. The final sample size of 1,500 per cohort will represent all pregnancies that met full inclusion/exclusion criteria. From this sample of livebirths and stillbirths, we conservatively estimate that at least 1,425 in each cohort will represent pregnancies ending in liveborn singleton infants.

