### 7.9.1. Study closure/uninterpretability of results

In consultation with the Scientific Advisory Board, discontinuation of the study will be considered at such time as:

- Sufficient information has accumulated to meet the scientific objectives of the study
- Other methods of gathering appropriate information become achievable or are deemed preferable
- The feasibility of collecting sufficient information diminishes to unacceptable levels because of low exposure rates, poor enrollment, or losses to follow up. Upon initiation of the study, recruitment is expected to continue for 4 years or until the target of 1,500 women exposed to *Boostrix* is reached, whichever comes first. Regular review of enrollment numbers will be performed. If target enrollment numbers are not being met, additional efforts will be implemented in marketing and awareness activities to achieve the targeted sample size.

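### The recruitment end rule counts only Boostrix-exposed women, so it permits, though nothing shows it likely, closure with fewer than the 1,500 comparators behind the stated study size

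*Protocol*

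**What the plan says.** The end of recruitment is described twice in the Protocol. Section 7.2.2: "recruitment of newly enrolled participants is expected to continue for 4 years, or until the target of 1,500 women exposed to" Boostrix is met, whichever is earlier. Section 7.9.1: "recruitment is expected to continue for 4 years or until the target of 1,500 women exposed to" Boostrix is met, with the same either-or. The comparator count appears in neither sentence.

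The size is set elsewhere, and for both cohorts:

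- Section 7.1: "The target sample size for the study by the end of a four-year recruitment period is 3,000 participants", split equally.
- Section 7.2.1: "An additional 1,800 participants (900 in each cohort) will be enrolled over four years", on top of about 600 per cohort already in the registry.
- Section 7.5: a comparator target of "1,500 women unexposed to any Tdap vaccine throughout their pregnancy", and "enrollment of 1,500 participants in each of the cohort groups is planned for completion within 4 years".
- Table 4: equal N in the two groups in every row (1,425 for preterm delivery and SGA, 1,469 for chorioamnionitis).

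If numbers lag, sections 7.2.2 and 7.9.1 provide for more awareness and marketing work. No minimum comparator number is given.

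**The concern.** The closing rule and the sample-size section describe different end points. The first is satisfied by one cohort and the second needs both. If the exposed cohort reached its target early, the rule as worded would end recruitment with time left in the four years and the comparator cohort possibly short. The marketing remedy would not help then, because it works only while recruitment is open.

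Some outreach is directed at vaccinated women. Section 7.2.2 states "The Sponsor will encourage exposed women or their Healthcare Providers to contact the Registry directly", and section 7.4 states "Healthcare providers are also informed that patients with Tdap exposure can be referred to the" registry. The feasibility argument in section 7.2.2 relies on how common Boostrix vaccination is and on total registry enrolment. It does not discuss the supply of unvaccinated women.

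At stake is the precision of every comparison. Chorioamnionitis is the Table 4 row with least room, and the Protocol already concedes limited power for stillbirth and the other secondary outcomes.

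**Working it through.** **1. Reproducing Table 4.** Inputs from Table 4: two-sided Fisher's exact test, alpha 0.05. Power is the sum, over both binomial distributions, of the probability of outcomes that the test rejects.

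- Chorioamnionitis: 1,469 per group, 3% against 3% × 1.7 = 5.1%. Power is 80.4%, which agrees with the stated 80%.
- Preterm delivery and SGA: 1,425 per group, 10% against 10% × 1.4 = 14%. Power is 89.9%. The smallest relative risk with 80% power is 1.344, so the stated 80% at 1.4 is conservative and these rows have reserve.

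**2. When would the exposed cohort fill first?** Let u be Tdap uptake and s the Boostrix share of doses among registry enrollees. Both cohorts start at about 600 and need 900 more. If enrollees arrive in proportion to their exposure, exposed women fill first when u × s > 1 − u, that is, when s > (1 − u)/u.

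- u = 55% (the national figure in section 5.1): s > 0.45/0.55 = 82%
- u = 70% (assumed): s > 0.30/0.70 = 43%
- u = 80% (assumed): s > 0.20/0.80 = 25%

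The Protocol says two Tdap brands are in use but gives no brand share, and it gives no uptake for the registry.

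**3. Comparator total when the 900th new exposed woman is reached.** Total = 600 + 900 × (1 − u)/(u × s). With s = 60% (assumed):

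- u = 55%: 600 + 900 × 0.45/0.33 = 1,827, so no shortfall
- u = 60%: 600 + 900 × 0.40/0.36 = 1,600, so no shortfall
- u = 70%: 600 + 900 × 0.30/0.42 = 1,243
- u = 75%: 600 + 900 × 0.25/0.45 = 1,100
- u = 80%: 600 + 900 × 0.20/0.48 = 975

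**4. Effect on power and precision.** Exposed N stays at its Table 4 value, and comparator N is scaled by total/1,500. The standard-error ratio for the log relative risk is √[(1/1,500 + 1/total) ÷ (2/1,500)], taking similar risks in the two cohorts.

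| Comparators enrolled | Chorioamnionitis, RR 1.7 | Preterm birth or SGA, RR 1.4 | SE ratio |
|---|---|---|---|
| 1,500 | 80.4% | 89.9% | 1.00 |
| 1,243 | 77.3% | 87.3% | 1.05 |
| 1,100 | 73.9% | 84.9% | 1.09 |
| 975 | 70.4% | 82.0% | 1.13 |
| 900 | 68.3% | 80.2% | 1.15 |

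These are unweighted calculations, as in Table 4.

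**The case against.** The strongest reply is that this is loose wording and not a decision to close with a short comparator cohort. The text says recruitment is expected to continue, the per-cohort targets are stated repeatedly, neither shortfall remedy is limited to exposed women, and enrolment is to be reviewed regularly. This stands as to intent. It does not remove the gap, because the only rule given for ending recruitment is still met by the exposed cohort alone.

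A second reply is that the Protocol's own figures make the exposed cohort the slower one. This also stands. At 55% uptake a very high Boostrix share is needed, and every shortfall scenario above uses a higher assumed uptake. The formula also counts every Boostrix recipient as exposed, whereas Cohort 1 requires documented Boostrix from week 27 onward. Women vaccinated only earlier enter neither cohort, which raises the required share further.

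A reader might infer from the sponsor and provider outreach that recruitment is directed only at vaccinated women. The Protocol does not support that. Section 7.2.2 names the teratogen information services as a primary referral source for unexposed women as well, much of the other publicity is not exposure-specific, and section 7.5 lets women enroll before the vaccination window. A reader might also infer that the primary power claims are at risk. In the scenarios shown they are not: preterm birth and SGA keep at least 80%.

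**Conclusion.** The inconsistency is real and minor. Sections 7.2.2 and 7.9.1 allow recruitment to end without 1,500 comparators, while the study size and Table 4 assume them. That this will happen is not shown: it needs a registry uptake or Boostrix share well above what the 55% figure suggests, and neither is documented for the registry.

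If it did happen, the measurable loss would fall on chorioamnionitis, from 80% to between 77% and 70% in the assumed scenarios. Stillbirth and the rare secondary outcomes, whose power the Protocol already calls limited, would have standard errors about 5% to 13% larger. These sizes rest on the assumed uptake values, a 60% Boostrix share, enrolment in proportion to exposure, and unweighted analysis.

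**What to change.** In sections 7.2.2 and 7.9.1, state that recruitment continues for 4 years or until 1,500 eligible women have been reached in both cohorts, whichever comes first. Eligible should mean meeting the full inclusion and exclusion criteria, which is how section 7.5 already counts the 1,500.

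The cost is two sentences. The targets and the four-year limit do not change. If comparators fill first, the new wording has no effect. If the exposed cohort fills first, the only downside is that recruitment may not close early.

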### 7.3. Variables

Variables for the exposures, outcomes, demographics, and clinical characteristics of interest are included below (Table 1 and Table 2). Data on these variables will be collected via maternal interview and medical record review per standard processes described in the OTIS/MotherToBaby Pregnancy Registry standard operating procedures. Detailed operational definitions will be provided in the Statistical Analysis Plan (SAP).

#### 7.3.1. Identification of Exposure and Comparator

Exposure is defined as any dose of US *Boostrix* on or after the 1st day of the 27th week of pregnancy, as reported by the mother or medical record. Detailed information regarding vaccine exposure status of participants is obtained through the maternal interviews and at the pregnancy outcome interview (0 to 6 weeks after the expected due date or end of pregnancy). Participants are directly queried about the specific vaccines they received, including information on the gestational timing, dates of exposure, and brand. Vaccine exposures are coded using the Slone Drug Dictionary. Maternal report that a Tdap vaccine was received is complemented by requesting medical records from the obstetric provider. Additionally, hospital of delivery, and pediatric medical records are requested for all participants.

A participant is classified as unexposed if she reports that she did not receive any Tdap vaccine, and her medical record shows no indication that she received any Tdap vaccine. A participant is classified as exposed if she reports in maternal interview that she received the *Boostrix* vaccine or if there is supporting documentation in the medical record for receipt of the *Boostrix* vaccine. If maternal report indicates no receipt of a *Boostrix* vaccine but the medical record indicates that the *Boostrix* vaccine was administered, the medical record will supersede maternal report and the participant would be classified as *Boostrix* vaccine-exposed. Moreover, where maternal report indicates that the *Boostrix* vaccine was received but documentation in the medical record is discordant (i.e., no indication in medical record that *Boostrix* vaccine was administered), the maternal report would supersede medical record for classification as exposed.

The estimated gestational weeks to qualify participants for the study for exposure and to classify outcomes is based on weeks from the first day of LMP which is counted as day 0. In circumstances where the date of LMP is not available or uncertain, or when a prenatal ultrasound estimates a gestational week that is discrepant according to obstetric guidelines, gestational week of pregnancy will be assigned based on the earliest available ultrasound (ACOG, 2017).

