## **Variables**

Exposure will be defined as receipt of the *Boostrix* vaccine confirmed by maternal report and/or medical record, with information on the gestational timing of administration and date of vaccination captured. Pregnancy and infant outcomes of interest include PTB, stillbirth, SGA infants, preeclampsia/eclampsia, PROM, chorioamnionitis, neonatal sepsis, neonatal death and NICU admission for bronchopulmonary dysplasia.

Information on study outcomes will be obtained by maternal report and/or medical record review. Potential confounders or covariates to be collected include maternal age, race/ethnicity, pre-pregnancy body mass index, socioeconomic status, pregnancy and health history, lifestyle factors, comorbidities, maternal exposures (including medication, vaccine, vitamin/mineral, and illnesses), and prenatal tests.

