## 5. RATIONALE AND BACKGROUND

### 5.1. Background

A US *Boostrix* pharmacovigilance pregnancy registry was initiated in 2005 ([Kuznetsova, 2022](#)) when *Boostrix* was licensed in the United States (US) for active booster immunization against diphtheria, tetanus, and pertussis (Tdap) in individuals aged 10 years and older. In June 2011, the US Advisory Committee on Immunization Practices (ACIP) recommended immunization of pregnant women against pertussis as a mean to protect their infants, who are vulnerable until they can receive their primary vaccination. ([CDC, 2013](#)). In October 2012, ACIP recommended that the Tdap vaccine be given to women during every pregnancy (preferably between 27–36 weeks gestation). Since 2014 the maternal Tdap uptake measured by surveys conducted by the US Centers for Disease Control (CDC) has plateaued at 55% ([Baïssas, 2021](#)). Two Tdap vaccine brands are used for immunization during pregnancy in the US ([CDC, 2017](#)).

The previous *Boostrix* US pregnancy registry EPI-PERTUSSIS-028 VS US PR (201327) was aimed at assessing the proportion with any abnormal pregnancy outcomes among registered pregnancies (women vaccinated with *Boostrix* during pregnancy or within 28 days preceding conception). From May 2005 to August 2019, 1,517 (1,455 prospective

and 62 retrospective) pregnancy reports were received from the pregnancy registry (Kuznetsova, 2022). Of the prospective reports, there were 1,188 lost to follow-up and 250 had known outcomes: 244 live infants with no apparent birth defects, 3 live infants with birth defects, and 3 spontaneous abortions with no apparent birth defects. Data from the *Boostrix* US pregnancy registry EPI-PERTUSSIS-028 VS US PR (201327) raised no safety concerns regarding *Boostrix* maternal immunization (Kuznetsova, 2022). However, the findings from the registry were limited by the modest number of follow-up reports (N=250) and the lack of representativeness of all pregnancies, the high proportion of loss to follow-up and the absence of a comparison cohort who were unexposed to Tdap vaccination during pregnancy.

On October 7 2022, the US Food and Drug Administration approved *Boostrix* for immunization during the third trimester of pregnancy to prevent pertussis in infants younger than two months of age (US FDA, 2022). This revised registry aims at monitoring the safety of *Boostrix* in this indication and is a postmarketing commitment.

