**Table 1 Exposure, Comparator and Outcome Variables**

Variable	Role	Data Source(s)	Operational Definition
Exposure to the Boostrix vaccine	Exposure	Maternal report, Vaccine record (e.g., yellow card), Medical record	Maternal report or medical record documentation of exposure to the Boostrix vaccine on or after the 1 st day of the 27 th week of pregnancy
Gestational timing of the Boostrix vaccine	Exposure	Maternal report Vaccine record (e.g., yellow card) Medical record	Maternal report or medical record documentation of the dates of the Boostrix vaccine administration on or after the 1 st day of the 27 th week of pregnancy
No Tdap vaccine exposure during pregnancy	Comparator	Maternal report Medical record	Maternal report of no exposure to any Tdap vaccine at any time from the first day of the LMP to the end of pregnancy; no documentation of Tdap vaccine in medical record
Preterm delivery	Primary Outcome	Maternal report Medical record	Maternal report and medical record documentation of a spontaneous or induced delivery after the 1 st day of the 27 th week of gestation or date of Boostrix vaccination, (whichever comes later) and <37 gestational weeks (as counted from the first day of LMP) (See Section 7.3.1 for operational definition of LMP) ( CDC, 2021 )
Stillbirth	Primary Outcome	Maternal report Medical record	Maternal report and medical record documentation of a non-deliberate fetal death that occurs after the 1 st day of the 27 th week of gestation or date of Boostrix vaccination, (whichever comes later), but prior to delivery ( Prager, 2021 )
Small for gestational age infant	Primary Outcome	Maternal report Medical record	Maternal report and medical record documentation of birth size for liveborn infants born after the 1 st day of the 27 th week of gestation or date of Boostrix vaccine, whichever comes later) (weight, length, or head circumference) $\leq 10^{\text{th}}$ percentile for sex and gestational age using NCHS pediatric growth curves for full term infants. Prenatal growth curves specific to preterm infants are used for preterm infants ( Olsen, 2010 ; Schlaudecker, 2017 )

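### Section 7.3.1 lets a mother's report of Boostrix override any record that does not show it, without separating a silent record from one that names the other Tdap brand

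*Protocol*

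**What the plan says.** Section 7.3.1 accepts either source for exposure. If the record shows Boostrix and the mother does not report it, the record prevails. If she reports it and the record is discordant, "the maternal report would supersede medical record for classification as exposed". The only explanation of discordance is "no indication in medical record that *Boostrix* vaccine was administered".

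The either-source definition appears in two other places. The abstract has exposure "confirmed by maternal report and/or medical record", and Table 1 has "Maternal report or medical record documentation of exposure to the Boostrix vaccine".

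Eligibility in section 7.2.1 is worded differently. Cohort 1 requires "documented exposure to *Boostrix* brand Tdap vaccination". For the roughly 600 previously enrolled pregnancies per cohort, a selection criterion is "If vaccinated, data available to document Tdap vaccination brand". Neither criterion says what kind of source counts as documentation.

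Section 5.1 notes that "Two Tdap vaccine brands are used for immunization during pregnancy in the US". Section 7.1 says that medical records are abstracted in order to validate exposures as well as outcomes.

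**The concern.** The research question is about one brand. Under 7.3.1 a record can move a woman into the exposed cohort but can never move her out once she has reported Boostrix. For a silent record that may be reasonable. For a record that names another product, it means that recall of a brand name outweighs a record of what was given, although the records were collected to validate exposure.

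Three things are at stake:

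- **Brand specificity.** Women given the other Tdap vaccine could be counted as Boostrix-exposed.
- **Direction of bias.** Any women in the exposed cohort who had no Tdap at all would tend to pull the relative risk towards 1. In a safety study that is the direction that hides harm.
- **Eligibility.** Staff cannot tell from the text whether a woman with only her own report satisfies the Cohort 1 criterion. Her start of follow-up, which is the vaccination date, also rests on that report.

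**Working it through.** **1. The rule applied case by case.** The mother reports Boostrix, on or after the start of week 27.

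| What the record shows | Class under 7.3.1 as written | Comment |
|---|---|---|
| Boostrix | Exposed | Sources agree |
| No Tdap entry | Exposed | Defensible: she may have been vaccinated elsewhere |
| Tdap, brand not given | Exposed | Record is silent on brand; her report supplies it |
| Only the other Tdap brand | Exposed, on a literal reading | Record contradicts the report on brand |

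The last three rows all meet the stated condition of no indication of Boostrix, and the rule treats them alike. Only the last has positive evidence of a different product.

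**2. Is it tested anywhere?** Section 7.7.2 covers changing preeclampsia criteria, previously versus newly enrolled women, restriction to influenza-vaccinated women, and exclusion of major birth defects. None of these varies the source of exposure data.

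**3. The plan's own power figures.** Inputs from Table 4: two-sided alpha 0.05, Fisher's exact test.

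- Chorioamnionitis, 1,469 per group, 3% in the comparison group, RR 1.7: exact Fisher power is 80.4%, against 80% stated. It reproduces.
- Preterm delivery (SGA has the same inputs), 1,425 per group, 10%, RR 1.4: exact Fisher power is 89.9%, against 80% stated. Power of 80% is reached at an RR of about 1.35, so the row agrees only if 1.4 is a rounded-up detectable value. That is a separate matter; it means that preterm power starts here from about 90%.

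**4. Dilution by women who had no Tdap.** Let m be the share of the exposed cohort that was in fact unvaccinated and has the comparison-group risk p0. The observed risk in the exposed cohort is (1 − m)·p0·RR + m·p0. Dividing by p0:

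observed RR = 1 + (RR − 1)(1 − m)

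At m = 10%: chorioamnionitis 1 + 0.7 × 0.9 = 1.63; preterm birth 1 + 0.4 × 0.9 = 1.36.

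The protocol gives no value for m. The range below is assumed.

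| m (assumed) | Chorioamnionitis: observed RR | Fisher power | Preterm/SGA: observed RR | Fisher power |
|---|---|---|---|---|
| 0% | 1.70 | 80.4% | 1.40 | 89.9% |
| 5% | 1.67 | 76.6% | 1.38 | 86.9% |
| 10% | 1.63 | 72.4% | 1.36 | 83.3% |
| 20% | 1.56 | 62.7% | 1.32 | 74.3% |
| 30% | 1.49 | 52.0% | 1.28 | 63.1% |

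For scale, m = 10% would mean 0.10 × 1,500 = 150 women in the exposed cohort who had no Tdap.

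**5. Dilution by women who had the other brand.** If a share m received the other brand, with relative risk RR_o, the observed value is (1 − m)·RR + m·RR_o. If RR_o = RR, this equals RR and there is no attenuation. If the two differ, the result is a mixture of two products.

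**The case against.** The case for the rule is substantial, and several stronger readings that a reader might infer are not supported.

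- **That 7.3.1 contradicts the eligibility criteria.** The abstract, 7.3.1 and Table 1 all accept either source, and 7.2.1 does not say that documentation must be a medical record. The texts can be read together. What remains is an undefined word, documented, on which entry to Cohort 1 turns.
- **That the protocol says recall beats an other-brand record.** It does not. The explanation of discordance most naturally describes a silent record. The other-brand case follows from the literal wording and the lack of an exception.
- **That the either-source rule for exposed and the both-sources rule for unexposed are an unfair asymmetry.** For silent records they are logical complements, and the second keeps vaccinated women out of the comparator.
- **That misclassification necessarily pulls the RR towards 1.** This holds for unvaccinated women at comparator risk. It need not hold for women given the other brand (step 5).
- **That record confirmation should define exposure in the main analysis.** A silent obstetric record does not show that no vaccine was given. Women are asked directly about brand and date, keep a diary, and enrol before the pregnancy outcome is known. Requiring a record would drop truly vaccinated women and select on record completeness. It trades sensitivity for specificity and does not correct an error.

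Section 7.3 leaves detailed operational definitions to the SAP, which is not at hand. But the precedence rule itself is fixed in the protocol, so it is fair to ask that it be fixed clearly there. The objections do not answer the one case in which the record positively names another product, nor the absence of any analysis by exposure source.

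**Conclusion.** The point holds in a limited form. As written, 7.3.1 does not distinguish a silent record from a contrary one, so it can assign the wrong product in a brand-specific study. It is also unreconciled with the documentation wording in 7.2.1, and no planned analysis would show whether it matters.

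The size is unknown. The power losses above depend on an assumed m, on those women having comparator-level risk, and on an unadjusted Fisher test. The planned preterm analysis is a Cox marginal structural model, so its figures are illustrative only. At m = 10%, preterm power is still 83%, above the 80% stated in Table 4. Chorioamnionitis has no such margin and falls to 72%. Since m counts women actually misclassified, it cannot exceed the discordant share and is smaller unless every discordant report is wrong.

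For women given the other brand, the likely loss is of brand specificity, not necessarily of effect size.

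**What to change.** 1. In 7.3.1 and Table 1, state that a woman whose medical or vaccine record for this pregnancy names another Tdap brand, with no record of Boostrix, enters neither cohort, whatever she reports. The Cohort 2 criteria already exclude her from the comparator.
2. Keep the either-source rule in the main analysis for records that are silent on Tdap or on its brand, after requesting the vaccine-provider record, which is already a listed data source.
3. Add to 7.7.2 a sensitivity analysis restricting the exposed cohort to women with Boostrix and its date confirmed in a record. Report how many women were classified by maternal report alone.
4. Define documented once, and use that definition in the 7.2.1 selection criteria, the Cohort 1 criteria, 7.3.1 and Table 1.

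Cost: a few women with contrary brand records are lost from the exposed cohort, some extra vaccine-provider requests are made, and one analysis is added. The main exposure definition is otherwise unchanged.
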